Hepatic	 Grade 3 or 4 bilirubin increase ALT or AST >8 × ULN In absence of liver metastases at baseline and in absence of clinical or radiological evidence of biliary obstruction: ALT or AST >3 × ULN, in conjunction with total bilirubin >2 ×ULN 	
Biochemistry	 Grade 4 Grade 3 lasting more than 7 days, unless considered not clinically significant as per the discretion of the investigator 	
Any other non- hematologic AE	Grade 4 Grade 3 (except diarrhea, rash, nausea, or vomiting lasting ≤72 hours) Any drug-related intolerable Grade 2 toxicity (other than hematological AEs) leading to administration of <75% of the dose during the DLT observation period	

AE = adverse event; ALT = alanine aminotransferase; ANC = absolute neutrophil count; AST = aspartate aminotransferase; CTCAE = Common Terminology Criteria for Adverse Events; DLT = dose-limiting toxicity; GM-CSF = granulocyte– macrophage colony-stimulating factor; ULN = upper limit of normal.

a. Laboratory values that meet criteria listed in this table should be repeated and confirmed within 24 hours of the initial results being reported.

Intrasubject dose escalation: Once a subject has completed Cycle 3 at her assigned dose level of drug, intrasubject dose escalation will be allowed. No more than 2 dose escalations are allowed for any subject. Only subjects who have not progressed on treatment and did not have a dose reduction of either palbociclib or H3B-6545 because of AEs can escalate to the highest dose level that has completed DLT assessment and has been shown to be safe (no more than 1 DLT in 6 subjects). Subjects on the intra-subject dose escalation will not be included in the DLT analysis at the higher dose level.

Dose expansion: An additional 12 subjects will be treated at the MTD/RP2D to further characterize safety, tolerability, and PK and to provide preliminary estimates of efficacy. In Cycle 1, subjects will receive palbociclib PO QD on Days 1 to 21 and H3B-6545 PO QD on Days 9 to 28. In all subsequent cycles, palbociclib will be administered on Days 1 through to 21 and H3B-6545 will be administered Days 1 through to 28.

AEs will be managed by treatment interruption, dose reduction, and/or treatment discontinuation in accordance with the dose modification instructions outlined in the protocol. Treatment will continue until disease progression, development of unacceptable toxicity, or withdrawal of consent.

Number of Subjects

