- The current cohort so that the total number of DLT-evaluable subjects is maintained at 6, if any of the 6 already dosed subjects becomes non-evaluable for DLT;
- A lower dose cohort which has already been deemed safe per dose escalation meeting, if none of the 6 already dosed subjects becomes non-evaluable for DLT in the cohort currently under evaluation; the additional subject(s) will not contribute to DLT evaluation of the lower dose cohort, but will contribute to the overall safety evaluation.
- The next cohort to be opened to enrollment including the expansion cohort if the RP2D has been reached and the expansion phase is open to enrollment.

Sponsor approval of any enrollment scenario not described above must take place prior to screened subject enrollment.

In the 1st cycle, palbociclib will be administered PO QD on Days 1 to 21 and H3B-6545 will be administered PO QD on Days 9 to 28. In all subsequent cycles, palbociclib will be administered on Days 1 to 21 and H3B-6545 will be administered Days 1 to 28.

A maximum of 4 dose levels are planned, with palbociclib escalated no higher than 125 mg QD and H3B-6545 escalated no higher than 450 mg QD (RP2D); see dose escalation in Table 3.

Dose Level (Cohort)	Palbociclib Dose (mg QD)	H3B-6545 Dose (mg QD)	Number of DLT- Evaluable Subjects
-1	75	300	6
1 (starting dose)	100	300	6
2	125	300	6
3	125	450	6
3b	100	450	6

Table 3Dose Escalation

DLT = dose limiting toxicity; QD = once daily.

Subjects will be assigned to a dose level in the order of study entry. DLTs will be assessed during the first 28 days starting from the 1st day of adding H3B-6545 to palbociclib (Cycle 1 Day 9 to Cycle 2 Day 8). Subjects who do not receive at least 75% of the scheduled therapy

from Cycle 1 Day 9 to Cycle 2 Day 8, for reasons other than toxicity, will not be considered evaluable for DLT assessment and will be replaced. Disease progression and AEs deemed related to disease progression will not be considered DLTs.

After all subjects in a cohort have completed the DLT observation period, all available safety data will be reviewed by the Safety Review Committee (SRC) consisting of sponsor personnel and investigators, and the decision to proceed to the next dose cohort will be made jointly.

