Dose escalation will proceed if <2 of 6 evaluable subjects experience a DLT and will continue until a dose level where ≥ 2 of 6 subjects experience a DLT. If ≥ 2 of 6 subjects in the starting dose cohort experience a DLT during the first cycle, then the dose level -1 will be explored.

The MTD is defined as the highest dose at which no more than 1 of 6 subjects experiences a DLT in the dose cohort. The RP2D may not exceed the MTD and will be agreed upon by the SRC based on an integrated evaluation of available safety, clinical benefit, PK, and pharmacodynamics (PD) data, for all dose levels tested.

DLT is based on the National Cancer Institute (NCI) Common Terminology Criteria for Adverse Events (CTCAE). DLT refers to toxicities experienced by subjects enrolled to the dose escalation portion of the trial during the first 2 cycles of treatment, which are at least possibly related to the study drug. A DLT will be defined as indicated in Table 4.

Toxicity	Criteria ^a		
Hematology	- Febrile neutropenia (ANC $<1\times10^{9}/L$ and fever ≥38.5 ° C)		
	- Grade 4 neutropenia that does not resolve to Grade ≤ 2 (ANC $\geq 1 \times 10^{9}/L$) within 7 days; use of GM-CSF is allowed		
	- Grade 4 thrombocytopenia (<25.0×10 ⁹ /L)		
	 Grade 3 thrombocytopenia (25.0 – 50.0×10⁹/L) lasting more than 7 days or associated with clinically significant bleeding 		
Vomiting	- CTCAE Grade 4 vomiting		
	- Grade 3 vomiting lasting >72 hours despite optimal antiemetic treatment		
Diarrhea	- CTCAE Grade 4 diarrhea		
	- Grade 3 diarrhea lasting >72 hours despite optimal antidiarrheal treatment		
Electrolytes abnormality	 Grade 4 Grade 3 lasting for more than 24 hours Note: Grade 3 that lasts <24 hours and resolves spontaneously or responds to conventional medical interventions is not considered a DLT. 		
Renal	- Grade 3 or 4 serum creatinine		
Hepatic	- Grade 3 or 4 bilirubin increase		
	- ALT or AST $> 8 \times ULN$		

Table 4 Definition of Dose-Limiting Toxicity

	- In absence of liver metastases at baseline and in absence of clinical or radiological evidence of biliary obstruction: ALT or AST >3 × ULN, in conjunction with total bilirubin >2 ×ULN
Biochemistry	 Grade 4 Grade 3 lasting more than 7 days, unless considered not clinically significant as per the discretion of the investigator

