Any other non- hematologic AE	Grade 4 Grade 3 (except diarrhea, rash, nausea, or vomiting lasting ≤72 hours) Any drug-related intolerable Grade 2 toxicity (other than hematological AEs) leading to administration of <75% of the dose during the DLT observation period

AE = adverse event; ALT = alanine aminotransferase; ANC = absolute neutrophil count; AST = aspartate aminotransferase; CTCAE = Common Terminology Criteria for Adverse Events; DLT = dose-limiting toxicity; GM-CSF = granulocyte–macrophage colony-stimulating factor; ULN = upper limit of normal.

a. Laboratory values that meet criteria listed in this table should be repeated and confirmed within 24 hours of the initial results being reported.

Intrasubject dose escalation: Once a subject has completed Cycle 3 at her assigned dose level of drug, intrasubject dose escalation will be allowed. No more than 2 dose escalations are allowed for any subject. Only subjects whose conditions have not progressed on treatment and did not have a dose reduction of either palbociclib or H3B-6545 because of AEs can escalate to the highest dose level that has completed DLT assessment and has been shown to be safe (no more than 1 DLT in 6 subjects). Subjects on the intrasubject dose escalation will *not* be included in the DLT analysis at the higher dose level.

Dose expansion: An additional 12 subjects will be treated at the MTD/RP2D to further characterize safety, tolerability, and PK and to provide preliminary estimates of efficacy. In Cycle 1, subjects will receive palbociclib PO QD on Days 1 to 21 and H3B-6545 PO QD on Days 9 to 28. In all subsequent cycles, palbociclib will be administered on Days 1 through to 21 and H3B-6545 will be administered Days 1 through to 28.

AEs will be managed by treatment interruption, dose reduction, and/or treatment discontinuation in accordance with the dose modification instructions outlined in the protocol. Treatment will continue until disease progression, development of unacceptable toxicity, or withdrawal of consent.

The data cutoff date for the primary analysis will be approximately 6 months after the last subject receives their first dose of study treatment. The end of study will be the last assessment for the last subject (eg, the last assessment for the last subject in the Extension Phase).

An overview of the study design and the decision rules for selection of the RP2D is presented in Figure 1.

Figure 1 Study Design and Selection of the Recommended Phase 2 Dose

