Grade 3 (symptomatic, intervention indicated)	Withhold palbociclib until (a) symptoms resolve and (b) heart rate is \geq 50 bpm; resume drug at the next lower dose	Withhold drug until (a) symptoms resolve and (b) heart rate is \geq 50 bpm; resume drug at the next lower dose
Grade 4 (Life-threatening consequences; urgent intervention indicated)	Withhold palbociclib until (a) symptoms resolve and (b) heart rate is \geq 50 bpm; resume drug at the next lower dose	Discontinue drug
QTcF prolongation		-
Grade 1 (average: 450 – 480 ms)	No dose adjustment is required	No dose adjustment is required

Grade 2	No dose adjustment is required	No dose adjustment is required
(average: 481 – 500 ms)		Repeat assessment after 1 week; if the average is still between 481 and 500 mg, decrease to the next lower dose
Grade 3 (average: ≥501 ms; >60 ms change from baseline)	Withhold drug until average is <480 ms and <60 ms change from baseline; resume at the next lower dose	Withhold drug until average is <480 ms and <60 ms change from baseline; resume at the next lower dose
Grade 4 (Torsade de pointes; polymorphic ventricular tachycardia; signs/symptoms of serious arrhythmia)	Discontinue drug	Discontinue drug
Other		
Grade 1 or 2	No dose adjustment is required	No dose adjustment is required
Grade 3 or 4 (if persisting despite optimal medical care)	Withhold palbociclib until symptoms resolve to Grade ≤2; resume drug at the next lower dose	Withhold drug until symptoms resolve to Grade ≤ 2 ; resume drug at the next lower dose

CTCAE = Common Terminology Criteria for Adverse Events; QTcF = QT interval corrected for heart rate using Fridericia's formula.

Monitor subjects for pulmonary symptoms indicative of ILD/pneumonitis (eg, hypoxia, cough, dyspnea). In patients who have new or worsening respiratory symptoms and are suspected to have developed ILD/pneumonitis, interrupt palbociclib immediately and evaluate the subject. Permanently discontinue palbociclib in subjects with severe ILD or pneumonitis.

Dose modifications for use with strong CYP3A inhibitors

Avoid concomitant use of strong CYP3A inhibitors and consider an alternative concomitant medication with no or minimal CYP3A inhibition. If patients must be co-administered a strong CYP3A inhibitor:

- Reduce the palbociclib dose to 75 mg QD
- Reduce the H3B-6545 dose to 150 mg QD

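### As written, the DLT table does not count a drug-related death with no earlier recorded qualifying event, yet the subject stays among the evaluable six

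*Protocol*

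**What the plan says.** Protocol Section 9.1 limits DLTs to toxicities at least possibly related to study drug and then hands over the definition: "A DLT will be defined as indicated in Table 4". The last row of Table 4, for any other non-hematologic AE, lists "Grade 4 Grade 3 (except diarrhea, rash, nausea, or vomiting lasting ≤72 hours" (two list items run together in the extracted text). It then adds "Any drug-related intolerable Grade 2 toxicity (other than hematological AEs) leading to administration of <75% of the dose". The Synopsis repeats the table.

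The count from this table drives three rules in Section 9.1:

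- Escalation proceeds if fewer than 2 of 6 evaluable subjects have a DLT.
- The MTD is "the highest dose at which no more than 1 of 6 subjects experiences a DLT".
- A dose is treated as safe for intrasubject escalation if at most 1 of 6 subjects had a DLT.

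On evaluability, subjects who receive less than 75% of scheduled therapy "for reasons other than toxicity, will not be considered evaluable for DLT assessment and will be replaced".

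SAP Section 3.2 takes its DLT definition from Table 4 of protocol version 5.0, Amendment 4.0. SAP Section 5.6.2 tabulates DLTs on that basis.

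**The concern.** Protocol Section 9.6.1.4.1 grades AEs on a 5-point scale, but no row of the DLT table reaches the fifth point or mentions death. A drug-related death that no listed row has already captured is therefore not a DLT on the wording. The subject is not replaced either, because her missed doses are due to toxicity. She sits in the denominator of six as a subject without a DLT.

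The error runs in the unsafe direction. It understates toxicity in the count that governs escalation, the MTD and the dose open to intrasubject escalation. It also sits oddly beside the Grade 2 criterion. A table that counts an intolerable Grade 2 toxicity because it cut dosing below 75% can hardly be meant to leave out a drug-related death. This looks like a wording omission.

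**Working it through.** **1. Reading the rows.** The plan states no error rate or operating characteristic for the DLT rule (Protocol Section 9.8.2 says that no formal sample size calculation was done), so there is no figure to reproduce. Table 4 and the Synopsis copy contain:

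| Row | Grades named | Criteria without a grade ceiling |
|---|---|---|
| Hematology | 4 (neutropenia, thrombocytopenia); 3 (thrombocytopenia, with conditions) | Febrile neutropenia |
| Vomiting, diarrhea | 4; 3 if over 72 hours | None |
| Electrolytes | 4; 3 if over 24 hours | None |
| Renal | 3 or 4 | None |
| Hepatic | 3 or 4 (bilirubin) | ALT/AST thresholds |
| Biochemistry | 4; 3 if over 7 days | None |
| Other non-hematologic | 4; 3 with exceptions; intolerable 2 | None |

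No row says Grade 5, Grade ≥3, fatal or death. The documents do not spell out that the top grade means death. The point does not depend on it, because neither a grade above 4 nor death appears.

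**2. What the table already catches.** These limits make the gap narrow:

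- Febrile neutropenia and "ALT or AST >8 × ULN" count whatever the outcome, if recorded.
- Investigators report increases in grade (Protocol Section 9.6.1.4.1), so an event that worsens will normally meet a row before death.
- Protocol Table 6 (Section 9.5) classes QTcF prolongation as "Grade 3 (average: ≥501 ms; >60 ms change from baseline" and arrhythmia as "Grade 4 (Torsade de pointes; polymorphic ventricular tachycardia; signs/symptoms of serious arrhythmia". If related and recorded, both enter through the catch-all row.

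What is left is a drug-related death in the DLT window with nothing qualifying recorded first, for example an unwitnessed sudden death.

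**3. Effect on the written count.** Let d be the number of such deaths in a cohort of six and t the number of other subjects with a listed DLT. The written count is t/6, the count with deaths included is (t+d)/6, and the limit is 2.

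| d | t | Written | Death counted | Crosses the limit? |
|---|---|---|---|---|
| 1 | 0 | 0/6 | 1/6 | No |
| 1 | 1 | 1/6 | 2/6 | Yes |
| 1 | 2 | 2/6 | 3/6 | No |
| 2 | 0 | 0/6 | 2/6 | Yes |
| 2 | 1 | 1/6 | 3/6 | Yes |
| 2 | 2 | 2/6 | 4/6 | No |

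**4. How often one death would matter to the count.** Given d = 1, the written count falls on the wrong side of the limit only if exactly one of the other five subjects has a listed DLT. With an assumed rate p, independent across subjects:

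P(exactly 1 of 5) = 5 × p × (1 − p)^4

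For example, p = 0.20 gives 5 × 0.20 × 0.80^4 = 0.410.

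| Assumed p | Crosses (t = 1) | No change, t = 0 | No change, t ≥ 2 |
|---|---|---|---|
| 0.05 | 0.204 | 0.774 | 0.023 |
| 0.10 | 0.328 | 0.590 | 0.081 |
| 0.167 | 0.402 | 0.402 | 0.196 |
| 0.20 | 0.410 (maximum) | 0.328 | 0.263 |
| 0.25 | 0.396 | 0.237 | 0.367 |
| 0.333 | 0.329 | 0.132 | 0.539 |

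So the range is 20% to 41%, conditional on one such death. The written count stays on the same side of the limit in the remaining 59% to 80%. The documents give no rate for such deaths, so no unconditional probability follows.

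**The case against.** **The committee would act.** Under Section 9.1 the Safety Review Committee reviews all available safety data and decides jointly, and the RP2D rests on an integrated evaluation. Section 9.8.3 makes continued enrollment depend on the totality of the data. This stands, and it makes harm unlikely. It does not alter the written count, the MTD definition or the SAP's DLT table. To stop on such a death, the committee would have to go beyond the stated definition.

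**Grades are ordered, so Grade 4 can be read as a minimum.** Table 6 describes Grade 4 bradycardia as life-threatening, and a fatal event has passed that level. This is probably what the authors meant. But the rows name grades as fixed points, whereas the protocol writes Grade ≥3 elsewhere (Section 9.5), as does the SAP (Section 5.6.3). The intent has to be supplied by the reader.

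**Deaths are reported anyway.** SAP Section 5.6.3 tabulates TEAEs leading to death, so the event would be visible. That table does not feed the DLT count.

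**Little now depends on it.** SAP Section 3.2 says that no expansion subjects will be enrolled, and the protocol's rationale for Amendment 04 says that further development is not planned. Both stand and limit the consequence. The documents do not say whether escalation enrollment was complete, so the practical use of an amendment is uncertain.

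A reader might infer that fatal toxicity in general escapes the DLT count. The documents do not support that: criteria without a grade ceiling and earlier recorded Grade 3 or 4 events capture most routes to a drug-related death. Nor do they support reading the omission as a deliberate exclusion.

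**Conclusion.** The gap is real but narrow, and minor. As written, a drug-related death in the DLT window with no earlier recorded qualifying event is a non-DLT in an evaluable subject. One such death alone changes only the reported count. Together with exactly one other DLT, it leaves the written count at 1/6 where 2/6 would stop escalation. Two such deaths with at most one other DLT have the same effect.

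The 20% to 41% might be taken as the chance of a wrong escalation decision. It is not. It is conditional on one such death having occurred, it rests on an assumed DLT rate of 5% to 33% in the other five subjects, and it supposes that the count is applied mechanically. The committee's full safety review makes that last step unlikely. Such a death is expected to be rare, though the documents give no rate.

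**What to change.** Add one row to protocol Table 4 and the same row to the Synopsis DLT table: *Any Grade 5 event, unless considered not related to study drugs or due to disease progression.* The two exclusions match those already in the DLT text. Adding (fatal) after Grade 5 would help, since the protocol does not say what the fifth grade is.

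The SAP would not pick up the new row by itself. Its Sections 3 and 3.2 are tied to protocol version 5.0, Amendment 4.0, so the reference to Table 4 must be updated to the amended protocol.

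The cost is one row in two tables and one SAP reference. The change has to go through a written protocol amendment under Protocol Section 11.1, with any regulatory and IRB/IEC submission that it requires; a change to the DLT definition plausibly requires both. No new data are needed, because deaths, grade and relatedness are already collected.

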9.5 Dose Modifications

Neutropenia was the most frequently reported adverse reaction in palbociclib clinical trials, with an incidence of 80% to 83%. A Grade \geq 3 decrease in neutrophil counts was reported in 66% of patients receiving palbociclib plus letrozole or fulvestrant. The median time to first episode of any grade neutropenia was 15 days and the median duration of Grade \geq 3 neutropenia was 7 days.

Febrile neutropenia has been reported in 1.8% of patients exposed to palbociclib across studies. Physicians should inform patients to promptly report any episodes of fever.

Management of severe or intolerable adverse reactions may require temporary dose reduction and/or interruption of palbociclib and/or H3B-6545.

Recommendations for dose reduction, interruption or discontinuation of either drug in the management of adverse reactions are summarized in Table 5 (hematologic toxicities) and

 Table 6 (non-hematologic toxicities).
 Clinical judgment of the treating physician should guide the management plan of each patient based on individual benefit/risk assessment.

Two dose reductions of H3B-6545 (450 mg to 300 mg, and then to 150 mg QD) for toxicity will be allowed as per the guidance summarized in Table 5 and Table 6. If persistent toxicity occurs despite 2 dose reductions, the subject will discontinue study treatment.

Two dose reductions for palbociclib (125 mg to 100 mg, and then to 75 mg QD) for toxicity will be allowed (Table 5 and Table 6). If persistent toxicity occurs despite 2 dose reductions, the subject will discontinue study treatment.

Hematologic toxicities

Monitor complete blood cell (CBC) counts prior to the start of palbociclib therapy and at the beginning of each cycle, as well as on Day 15 of the first 2 cycles, and as clinically indicated. For patients who experience a maximum of Grade 1 or 2 neutropenia in the first 6 cycles, monitor CBC counts for subsequent cycles every 3 months, prior to the beginning of a cycle and as clinically indicated.

CTCAE Grade	Palbociclib	H3B-6545
Anemia		
Grade 4	Withhold dose until recovery to Grade ≤2; resume drug at next lower dose	Withhold dose until recovery to Grade ≤2; resume drug at next lower dose

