9.6.1.4.3 LABORATORY MEASUREMENTS

Clinical laboratory tests to be performed, including hematology, chemistry, and urinalysis, are summarized in Table 7. Subjects should be in a seated or supine position during blood collection. The Schedule of Procedures/Assessments (Table 8) shows the visits and timepoints at which blood for clinical laboratory tests and urine for urinalysis will be collected in the study.

Category	Parameters
Hematology	Hematocrit, hemoglobin, platelets, RBC count, and total WBC count with 5-part differential
Coagulation	INR, PT, aPTT
Comprehensive metabolic panel	Fasting glucose, calcium, albumin, total protein, electrolytes (sodium, potassium, carbon dioxide, chloride), renal function tests (blood urea/blood urea nitrogen, creatinine), liver function tests (ALP, ALT, AST, bilirubin)
Other	Albumin, CRP, fasting lipase, fasting amylase, lactate dehydrogenase, magnesium, phosphorus, gamma-glutamyl transpeptidase, and thyroid function tests (TSH and free T ₄)
Virology	HBV, HCV, HIV
Urine dipstick	Bacteria, casts, crystals, epithelial cells, glucose, ketones, occult blood, pH, protein, RBCs, specific gravity, WBCs

Table 7 Clinical Laboratory Tests

ALP = alkaline phosphatase; ALT = alanine aminotransferase; aPTT = activated partial thromboplastin time; AST = aspartate aminotransferase; CRP = C-reactive protein; HBV = hepatitis B virus; HCV = hepatitis C virus; HIV = human immunodeficiency virus; INR = International normalized ratio; PT = prothrombin time; RBC = red blood cell; T₄ = thyroxine; TSH = thyroid-stimulating hormone; WBC = white blood cell.

Central laboratory will be used for PK/PD and biomarker assessments. For all safety assessments (eg, liver and kidney function, blood count), the sites will use local laboratories.

All hematology, blood chemistry (including pregnancy test, as applicable), and urinalysis samples are to be obtained prior to study drug administration, and results will be reviewed prior to administration/dispensing of study drug at the beginning of each treatment cycle.

A laboratory abnormality may meet the criteria to qualify as an AE as described in this protocol (see Section 9.6.1.4.1 and the CRF Completion Guidelines). In these instances, the AE corresponding to the laboratory abnormality will be recorded on the Adverse Event CRF.

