9.6.2 Schedule of Procedures/Assessments

9.6.2.1 Schedule of Procedures/Assessments

Table 8 presents the schedule of procedures/assessments for the dose escalation and dose expansion phases of the study. Table 9 presents the procedures during the Extension Phase.

Period	Screening	Cycle	1				Cycle 2			Cycle 3+	ЕОТ	Safety Follow-	Survival ^a Follow-up
Day	D-21 to D1	D1 ^b	D8	D15	D21	D28±1 ^{cv}	D1	D8	D15	D1	-	up 28 days (+7 days)	
Procedure						•							
Informed consent	X												
Eligibility criteria	X												
Medical history	X												
Concomitant medication/ adverse events	X	X	X	X	X	X	X	X	X	X	X	X	
Physical examination ^d	X	X	X	X	X	X	X	X	X	X	X	X	
ECOG performance status	X	X					X			X	X	X	
Triplicate 12-lead ECG ^e	X	X	X	X	X	X	X			X	X	X	
ECHO or MUGA scan ^f	X									X			
Pregnancy test ^g	X						X			Х	X		
Laboratory													
CBC ^h	X	X	X	X	X	X	X	X	Х	Х	X	X	
CMP ⁱ	X	X		X			X		X	X	X	X	
Other ^j	X	X		X			X		X	X	X	X	
INR/PT/aPTT ^k	X						X			X	X	X	

Table 8 Schedule of Procedures/Assessments in Study H3B-6545-G000-102

Period Screening		Cycle	Cycle 1 Cycle 2 Cycle 3+						ЕОТ	Safety Follow-	Survival ^a Follow-up		
Day D-21 to D1	D1 ^b	D8	D15	D21	D28±1 ^{cv}	D1	D8	D15	D1	-	up 28 days (+7 days)		
Virology (HCV, HBV) ^l	X												
Urine testing dipstick ^m	X						X			X	X	X	
Study treatments dispensing/return ⁿ		X					X			X	X		
PK samples ^o			X		X	X					X		
PG whole blood	X												
Biomarkers and exploratory analysis	·					·		,		·		·	
Tumor biopsy ^p	X												
cfDNA whole blood ^q	X	X								X	X		
Efficacy								•					
PET scan or whole body bone scan ^r	X	Every	24 wee	ks in conji	unction wi	ith the schedu indicat	uled tumo	r assessme	ent visit or	as clinically			
CT/MRI scans ^s	X	E	Every 8 v	weeks unti	il radiolog	ical disease p	progressio	n and as c	linically in	dicated	X		
Brain scan ^t	X				As clinica	lly indicated	and to con	nfirm CR			X		
Survival follow-up ^u													X

Table 8 Schedule of Procedures/Assessments in Study H3B-6545-G000-102

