5.6.2 Dose Limiting Toxicity Data

In the Dose-Evaluable Set, the number (percentage) of subjects with DLTs will be presented by treatment groups. A listing of subjects with DLTs will be provided.

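### Table 4 scores dose loss below 75% as a DLT only for Grade 2 toxicity, so a short Grade 3 event that stops dosing can be scored DLT-free

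*Protocol*

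**What the plan says.** Four parts of the plan bear on this.

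- **Dose-loss criterion.** The last row of Table 4 (Protocol 9.1, repeated in the Synopsis) makes this a DLT: "Any drug-related intolerable Grade 2 toxicity (other than hematological AEs) leading to administration of <75% of the dose during the DLT observation period". No other row refers to the amount of drug received.
- **Grade 3 exemptions by duration.** The biochemistry row counts "Grade 3 lasting more than 7 days, unless considered not clinically significant as per the discretion of the investigator". The last row exempts Grade 3 diarrhea, rash, nausea or vomiting that lasts no more than 72 hours.
- **Evaluability.** Section 9.1 sets a minimum of 75% of scheduled therapy over the observation window (Cycle 1 Day 9 through Cycle 2 Day 8). Subjects who fall short of it "for reasons other than toxicity, will not be considered evaluable for DLT assessment and will be replaced". Dose loss caused by toxicity therefore stays among the six.
- **Decision rule and reporting.** Escalation proceeds when fewer than 2 of 6 evaluable subjects have a DLT, and the MTD uses the same limit. SAP 5.6.2 gives the count by treatment group and adds: "A listing of subjects with DLTs will be provided".

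Protocol 9.6.5 requires discontinuation for intolerable toxicity, or for abnormal laboratory values attributed to drug toxicity. It sets no minimum grade or duration.

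**The concern.** The dose-loss row exists to catch events that are not severe enough to be DLTs by grade but still prevent adequate dosing. As worded, it ranks two cases the wrong way round. A subject with an intolerable Grade 2 event who receives less than 75% of dosing has a DLT. A subject with a Grade 3 event that is exempt by duration, and who loses the same share of dosing or is taken off treatment, has none. That second subject is not replaced either, so she counts as one of six who tolerated the dose.

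The primary endpoint is the MTD and/or RP2D, and the written rule turns on a single subject: 1 of 6 passes and 2 of 6 does not. An omission of this kind can only make a dose look more tolerable.

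**Working it through.** The plan states no sample size, power or error rate for this rule, so there is no design figure to reproduce. The check is whether an exempt Grade 3 event can bring dosing below 75%.

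**Inputs (Protocol 9.1).** The window is Cycle 1 Day 9 to Cycle 2 Day 8. In Cycle 1, palbociclib is given on Days 1 to 21 and H3B-6545 on Days 9 to 28. In Cycle 2, both start on Day 1.

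**Scheduled doses in the window.**
- Length: 20 days of Cycle 1 + 8 days of Cycle 2 = 28 days, which agrees with the protocol.
- H3B-6545: 20 + 8 = 28 doses.
- Palbociclib: 13 (Days 9 to 21) + 8 = 21 doses.
- Both: 28 + 21 = 49 doses.

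**Discontinuation.** Suppose both drugs stop before dosing on Cycle 1 Day 15, a scheduled chemistry day, so that six doses of each have been taken. The fraction received is 6/28 = 21.4% for H3B-6545, 6/21 = 28.6% for palbociclib and 12/49 = 24.5% for both. If the Grade 3 event then resolves within its exempt duration, the subject is evaluable and DLT-free under Table 4.

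**Holds, by dose count.** Fraction received = (scheduled − missed)/scheduled.

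| Doses of each drug missed | H3B-6545 | Palbociclib | Both |
|---|---|---|---|
| 3 | 25/28 = 89.3% | 18/21 = 85.7% | 43/49 = 87.8% |
| 5 | 23/28 = 82.1% | 16/21 = 76.2% | 39/49 = 79.6% |
| 6 | 22/28 = 78.6% | 15/21 = 71.4% | 37/49 = 75.5% |
| 7 | 21/28 = 75.0% | 14/21 = 66.7% | 35/49 = 71.4% |

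- H3B-6545 alone does not fall below 75% with a hold of seven days or less; 21/28 is exactly 75%.
- Palbociclib alone falls below 75% once six doses are missed. Because of its off-week, a six-day hold does this from 11 of the 28 possible start days and a seven-day hold from 12.
- With both drugs counted together, six days is not enough. Seven days is enough from 11 start days.
- A 72-hour event costs about three doses and cannot reach the threshold by itself. The diarrhea, rash, nausea and vomiting exemptions matter only on discontinuation, or if the hold outlasts the event.

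**Which biochemistry is left.** Electrolytes, creatinine, bilirubin and transaminases have their own rows. What remains is mainly glucose, gamma-glutamyl transpeptidase and part of the Other group in Table 7 ("Albumin, CRP, fasting lipase, fasting amylase, lactate dehydrogenase, magnesium, phosphorus"). Table 8 schedules these tests inside the window only on Cycle 1 Day 15 and Cycle 2 Day 1. For an event of at most seven days, missing six palbociclib doses means that the hold starts by the event's second day or continues past recovery.

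**Effect on the decision.** One unscored event changes the outcome only when exactly one DLT was scored (1/6 becomes 2/6). With none scored, one more still passes. With two or more scored, the cohort has already failed.

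**The case against.** The best case against acting is that the gap is nearly empty and already supervised.

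- Under Protocol 9.6.1.4.1, a laboratory abnormality that belongs to a clinical syndrome is reported as that syndrome. At Grade 3 it then falls in the last row of Table 4, with no seven-day allowance. An event that declines to an intolerable Grade 2 and keeps costing doses may also be caught by the existing row. Both points stand and shrink the gap. What remains is mostly an isolated short laboratory abnormality, or a brief gastrointestinal event or rash that ends treatment. A laboratory value that nobody calls intolerable would stay unscored even after the change.
- The Safety Review Committee sees all available safety data, and the RP2D rests on an integrated evaluation. This is a real safeguard, but the written escalation and MTD rules use DLT counts.
- Applying the evaluability rule already requires someone to decide, subject by subject, whether dosing fell below 75% and why. SAP 5.6.1 lists dosing and the reasons for modification, and SAP 5.6.3 tabulates events leading to reduction or interruption. The facts can therefore be recovered. However, no planned output sets them beside the window, the threshold and the DLT call.

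Three stronger readings are tempting, and the documents do not support them.

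- *That a hold of a day or so opens the gap once dose is counted in mg after a step-down.* Table 6 reduces the dose for other nonhematologic toxicity at "Grade 3 or 4 (if persisting despite optimal medical care"), subject to clinical judgment. An event that is over in a day hardly meets that condition.
- *That the 75% threshold has no meaning.* Section 9.1 and Table 5 footnote b state the same evaluability rule, one in terms of scheduled therapy and the other in terms of the dose. Scheduled combination therapy is the natural reading, so what is missing is counting detail.
- *That cohorts have passed too easily.* The documents give no rate for such events, and it may be zero.

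**Conclusion.** The concern holds in a narrow form. By the written rule, a drug-related Grade 3 non-hematologic event that is exempt by duration can cost a subject more than 25% of her dosing, or end her treatment, and leave her evaluable and DLT-free. A Grade 2 event with the same loss would be a DLT. Nothing else in the protocol or SAP closes this. Reading the general Grade 3 line as covering short biochemistry events would cancel the seven-day allowance in the biochemistry row.

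The gap is clearest on discontinuation. For holds it depends on the count used: it opens at six missed palbociclib doses or a seven-day hold of both drugs, and not on an H3B-6545 hold of up to seven days. These figures assume dosing otherwise as scheduled and a count of doses, not mg. No effect on the probability of passing a cohort is claimed. This is a cheap correction to a rule that feeds the primary endpoint, not evidence that any dose decision was wrong.

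**What to change.** **If any cohort is still to be judged**, amend the row in Table 4 and the Synopsis in three places:

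1. Replace Grade 2 with Grade 2 or higher.
2. Add that this includes Grade 3 events otherwise exempt by duration.
3. Express the 75% as a share of the scheduled doses in the observation period, counted as number of doses. Say whether the two drugs are counted separately or together, since six missed days of both is 71.4% for palbociclib but 75.5% combined.

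Keep the requirement that the toxicity be drug-related and intolerable, and keep the clinical-significance exemption for biochemistry. Keep the hematologic exclusion too: Protocol 9.5 reports that a Grade 3 or higher "decrease in neutrophil counts was reported in 66% of patients receiving palbociclib plus letrozole or fulvestrant", with a median duration of 7 days.

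**If escalation is complete**, do not redefine DLTs after the fact. SAP 3.2 suggests that this may be so: it ties the data cutoff to the last subject of the escalation part and says that nobody will be enrolled in the expansion. In that case, add to SAP 5.6.2 a listing of Dose Evaluable subjects whose dosing fell below 75% in the window because of toxicity, with the event, its grade and the DLT call. An empty listing would settle the matter.

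The cost is a one-row wording change, or one listing from data already collected. The downside of the wording change is that a few more events may count as DLTs.
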